1. To examine feasibility of implementing a simplified physical examination (SPE) aimed at identifying patients suited to cervical spine OMT and neuromuscular/ sensorimotor retraining, within a New Zealand Primary Health Care setting.
2. Based on response to treatment over time, to provide preliminary evidence regarding the

efficacy of the simplified physical examination to accurately identify individuals who may be suited to physiotherapeutic intervention consisting of OMT and neuromuscular/sensorimotor retraining. Included in this objective will be use of data to validate a clinical objective oculomotor screen to improve clinical utility of the SPE.

We hypothesise that using the SPE will aid in identification of individuals suited to orthopedic manual therapy of the neck. Consequently, primary outcomes including clinician attitude toward using the SPE in a primary health care setting, and participant compliance and satisfaction with the OMT intervention will be positive. Further we anticipate that measurable improvement (objectively assessed neck function and clinical presentation) in response to the selection to neck OMT based on the SPE will be observable over time. Results will therefore support feasibility of using the SPE for acute patient assessment, as well as the clinical efficacy of this approach for managing neck related signs and symptoms following concussion.

Methods

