Volunteers who: respond to advertisement i) using the online screening questionnaire relating to the inclusion/exclusion criteria (primarily whether they have sustained a medically diagnosed concussion within the last 14 days); ii) the study phone; iii) the study email, or who are referred by a health practitioner will be contacted by the study SC. The SC will further screen them for inclusion and exclusion criteria. If eligible to participate in the screening session participants will be forwarded an electronic participant information sheet and consent form and scheduled for the screening session. Individuals contacting the SC in response to advertising who meet exclusion criteria at any stage of the screening process will be provided with names and contact details of primary health services for concussion in Dunedin for follow up if desired. Those recruited via advertisement will be requested to obtain written confirmation of their concussion from their treating physician.

Inclusion criteria: Adults aged 18-60 years, biological sex: male, female, who have sustained a medically diagnosed concussion (mild Traumatic Brain Injury) based on published diagnostic criteria [13-15] and are not more than 14 days since injury [14].

Exclusion criteria: Individuals with past or current history of:

- Moderate to severe TBI as defined by published diagnostic criteria [16]
- Diagnosed concussion with associated trauma related abnormalities apparent on CT or MRI and/ or cervical spine fracture
- Diagnosed concussion due to assault
- Neck pain unrelated to concussion injury(/ies) (requiring treatment)
- Headache disorders (including cervicogenic, migraine (chronic), and tensions type headaches)
- Vestibular, oculomotor, neurological disorders
- Major psychiatric disorders currently being actively treated
- Physical injury that would prevent completion of the screening session

Study power:

Based on previously identified rates of neck impairment post-concussion [9, 17] it is anticipated that screening of **160** participants will be required to identify **60** individuals who meet inclusion criteria. Allowing for 50% of individuals to decline participation in the trial and a 10% drop-out rate, it is anticipated that data from **n=27** participants (treatment commenced with **n=30**) will be collected at all data collection time points. This group size is consistent with those currently used in randomised control trials investigating outcome following OMT of the

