neck post-concussion [18] and with recommendations regarding pilot data sample sizes [19] so is considered adequate for this feasibility study.

Screening and Eligible Participant Identification Process:

Screening session procedure: The screening session will take place at the School of Physiotherapy research laboratories and will be conducted by the PI. Prior to attending the screening session participants will be sent a link by the SC to complete the battery of online questionnaires and asked to complete them 1 day prior to attendance. Included in the battery will be an electronic version of the consent form which participants will be required to sign prior to being able to access the questionnaires.

Questionnaires:

- Rivermead Post-concussion Symptoms Questionnaire (RPQ) [20] *13 Item and 3 Item* – Originally developed to provide an overall symptom severity measure based on symptom reporting following concussion. Participants rate the degree to which each symptom poses more of a problem since their head injury on a 0 to 4-point scale. When divided into three and thirteen item symptom scales construct validity was calculated at 0.83 for the 13-item questionnaire and 0.62 for the 3-item. IRR was 0.89 and 0.72 respectively [21]
- Neck Disability Index (NDI) [22] a 10 item scaled questionnaire. Each question requires the participant to select a response which most accurately reflects the difficulty they experience with specific functional tasks such as driving, reading working or sleeping, and also the extent to which they experience difficulty with function due to headache. It is currently utilised in cervical dysfunction populations including Whiplash Associated Disorder and neck pain to identify functional limitations resulting from either condition. Test-retest reliability has been established at 0.89 [22].
- Dizziness Handicap Index (DHI) [23] lists 25 functional activities. Individuals are asked to rate how much dizziness or unsteadiness affects performance of listed activities in terms of frequency. When summed the greatest resultant total scores for each of the subcategories; functional, emotional, or physical is determined to be the underlying causes for dizziness. Interrater reliability for the DHI has been calculated at 0.97 and internal consistency established between 0.72 and 0.85 for each of the categories [23]

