Up to 10 health practitioners involved in the referring, assessing, and treating of study participants will be invited to participate in focus groups (n=2, 5 participants per group). They will be asked to complete a brief demographic questionnaire (including questions related to age, biological sex, number of years and scope of practice). Four of these individuals will be further invited to attend one-on-one semi-structured interviews. Focus groups will be used to determine health practitioner attitudes toward ease of use (including any challenges), and perceived effectiveness (acceptability and usefulness) of the SPE to identify individuals

appropriate for neck rehabilitation (Orthopedic Manual Treatment (OMT) and neuromuscular/sensorimotor retraining) following concussion, and utility of this method in the context of current practice. All focus group and interviews will be recorded using a digital voice recorder, which will be transcribed for analysis. All transcriptions will be checked and anonymised by the SC. Based on coding and thematic analysis of transcribed recordings of focus group proceedings the study team will iteratively determine main themes to be further explored in semi-structured interviews. Co-investigators of the study will conduct all focus groups and interviews. All academic members of the study team have experience in qualitative research.

Focus groups and interviews will be held at the University of Otago research rooms. Prior to participation in the focus groups, attending health practitioners will have the purposes of the focus group/ interviews explained and will provide written consent. All participants will be reimbursed at \$120 per hour voucher to recognise the reasonable costs involved with participating in this study. Reimbursement for attendance at interviews will be provided in addition to reimbursement for attendance at focus groups.

Outcome Measures and Analysis:

Primary Outcomes: Feasibility

Qualitative data: focus groups and interviews

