Clinical data will be entered directly into the study's online data recording form which only the PI, SC and members of the research team will be able to access. Data in this form will be stored under a unique identifier generated during the initial screening session with the SC. Where raw data requires further analysis, it will be deidentified (VR and VNG outcomes) and routinely uploaded to the PIs (OG) password protected laptop or the password protected study laptop. Data collected using VR and VNG will be collected on the devices using the participants unique identifier.

Statistical Analysis

Descriptive analyses will be performed on sociodemographic data. Exploration of central tendency of all data will be evaluated using Kolmogorov-Smirnov and Shapiro-Wilk tests. Where data is significantly skewed, attempts will be made to transform using suggested methods [57]. Individual demographic variables (sex, age, BMI, IPAQ score) which could reasonably be expected to influence quantitative outcomes will be analysed for significance using univariate linear regression and included in models.

Objective 1:

Quantified feasibility outcomes: activity, compliance, and adverse event monitoring

- a. Descriptive statistics will be used for recruitment frequency and the number of eligible participants, the drop-out rate, and degree of missing data for the patient rated and clinical outcomes measures. The programme will be considered feasible if 80% of patients complete the programme until formal discharge based on the physiotherapists' assessment and treatment documentation.
- b. Adherence to the intervention by auditing and summarising patients' logbooks and the physiotherapists' assessment and treatment documentation. The SC will audit the documentation. Adherence will be considered acceptable if 80% of exercises had been recorded in the patient's logbooks.
- c. Adverse events from the treatment will be determined by auditing the physiotherapists' assessment and treatment documentation as well as inclusion of formal reports submitted to the study or HEC in the event of serious adverse events. Number of events will be considered.
- d. Patient satisfaction score (/12) from the patient satisfaction exiting questionnaire will be calculated and mean and 95% CI will be reported.

Triangulation of qualitative (analysis described above) and quantitative outcomes [79] will determine overall feasibility of using the SPE to inform treatment management.

Objective 2:

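### Objective 1 asks whether the simplified physical examination (SPE) is feasible in primary care, but study staff perform it only in a laboratory and every numeric feasibility threshold concerns the later treatment

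*Protocol*

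**What the plan says.** The first item under Study Objectives is "To examine feasibility of implementing a simplified physical examination (SPE) aimed at identifying patients suited to cervical spine OMT" and neuromuscular or sensorimotor retraining, "within a New Zealand Primary Health Care setting".

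On where the SPE is done, Screening session procedure states: "The screening session will take place at the School of Physiotherapy research laboratories". That section gives the task to the principal investigator (PI), while Eligibility for Entry to Treatment Arm describes the study coordinator (SC) as conducting the session. The follow-up SPEs take place in the same laboratories.

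Statistical Analysis, Objective 1, lists four quantitative items:

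- **Item a** describes recruitment, eligible numbers, drop-out and missing data, and then sets the rule: "The programme will be considered feasible if 80% of patients complete the programme until formal discharge", judged from the physiotherapists' records.
- **Item b** sets an 80% threshold for exercises entered in patients' logbooks.
- **Item c** begins "Adverse events from the treatment will be determined by auditing" and relies on the physiotherapists' records plus formal reports of serious events.
- **Item d** is a satisfaction score.

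The section closes by saying that triangulating qualitative and quantitative results will determine the overall feasibility of using the SPE. The qualitative part explores "health practitioner attitudes toward ease of use (including any challenges", together with perceived effectiveness and utility in current practice.

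**The concern.** The object of the objective and the object of the criteria differ. The objective is about an examination and a setting. The thresholds are about a course of physiotherapy given after that examination, in the subset who qualified and accepted.

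Two properties matter most for implementing an examination: whether patients tolerate it and how long it takes. The protocol raises both itself. Its ethical sections for the neck and vestibular measures warn of increased dizziness, nausea or neck soreness. Its Background criticises existing assessment as slow and liable to provoke symptoms, and says the SPE takes less time. Neither property is a feasibility outcome.

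The results are meant to inform a later pilot randomised trial. If the report concludes that the SPE is feasible in primary care, that trial would be planned on a claim that this study did not test.

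**Working it through.** **1. The planned flow (Study power).** Inputs: 160 screened, 60 eligible, 50% decline, 10% drop-out.

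- Yield: 60/160 = 37.5%.
- Starters: 60 × (1 − 0.50) = 30.
- Data at all time points: 30 × (1 − 0.10) = 27.

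The protocol's figures of 30 and 27 are reproduced.

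**2. Denominator of the 80% rule.** The text says only patients. Completion to discharge is read from physiotherapists' records, which exist only for people who began treatment. If all 60 eligible people were the denominator, the planned decline would cap the result at 30/60 = 50%, so 80% could never be reached. Starters is therefore the only workable reading. It is an inference and should be stated.

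**3. What the rule can see.** The pass mark is 0.80 × 30 = 24 completers. Those 24 are 24/60 = 40% of eligible people and 24/160 = 15% of those examined. Yield and uptake do not enter. For illustration, assume 20% yield and 25% uptake: 160 × 0.20 × 0.25 = 8 starters, and 7/8 = 87.5% still passes.

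**4. What each quantitative item covers.**

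| Item | Concerns | Threshold | Covers SPE tolerance or duration? |
|---|---|---|---|
| a, descriptive part | Recruitment, eligible numbers, drop-out, missing data | None | No |
| a, rule | Programme completion | 80% | No |
| b | Home-exercise logging | 80% | No |
| c | Treatment adverse events | None | No |
| d | Satisfaction; all four questionnaire items ask about the physiotherapy | None | No |

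Item c looks for treatment events. On the plan, 160 − 30 = 130 of the 160 people given the SPE (81%) never start treatment, so no treatment record exists for them. For the 30 starters, the records begin up to 2 weeks after the SPE. The protocol gives one hour as the estimated SPE time but does not list the actual time as an outcome.

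**5. Who has used the SPE.** It involves a virtual-reality headset and video-nystagmography goggles. The SC needs training from the PI in testing, data reduction and analysis. Treating physiotherapists receive a posted report and carry out a different, extended neck assessment. Study Procedure and Setting lists the interviewees as referrers, the study coordinator and treating physiotherapists. Of these, only the SC is described as performing the SPE. Assuming one SC, that is one person among up to 10 participants.

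**6. Should the planning values become pass marks?** Exact 95% intervals at the planned values are 30.0% to 45.5% for yield (60/160) and 36.8% to 63.2% for uptake (30/60). If the true rates equal the planning values, P(X ≥ 60 | n = 160, p = 0.375) = 0.53 and P(X ≥ 30 | n = 60, p = 0.50) = 0.55. With fixed denominators and independence, both are met with probability 0.53 × 0.55 = 0.29. A study running exactly to plan would usually fail, so these values are unsuitable as thresholds.

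**The case against.** The strongest reply is that the protocol does not let the 80% rule decide SPE feasibility. The rule judges the programme, and overall SPE feasibility is assigned to triangulation with practitioner data. That stands. A reader might infer that the 80% rule alone could declare the SPE feasible, but the text does not support this. What remains is that triangulation has no stated rule for combining its sources, and that its quantitative inputs omit SPE tolerance and duration.

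Second, item a already reports recruitment and eligible numbers. Its missing-data summary covers clinical outcome measures, which include most SPE tests. So yield, and part of test completion, would be visible. That also stands: these lack a defined role in the judgement, not coverage.

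Third, SPE reactions are not wholly unrecorded. Symptom increase on the vestibular/ocular motor screen is an experimental outcome, and Potential problems gives a contact route and a general adverse-event process. Neither is listed among the Objective 1 outcomes.

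Fourth, referrers and treating physiotherapists can speak to usefulness and acceptability, and the SC can speak to use. Objective 2 also aims to validate a clinical oculomotor screen, so the equipment problem is partly recognised. This is fair, but it does not place the SPE in primary care within this study.

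A reader might also take the 27 in Study power as programme completers and score the rule with it. The documents do not support that: 27 is the number with data at every time point, including the 3-month follow-up, not the number reaching discharge.

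**Conclusion.** The point holds as a mismatch between objective and evidence. The study can show whether people referred from primary care can be examined in a laboratory and whether those who start treatment complete it. It cannot show that the SPE can be implemented in primary care, because no primary-care clinician is described as performing it.

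Both numeric thresholds and the adverse-event count concern treatment in a planned 30 of 160 people examined (19%). SPE tolerance and duration have no quantitative feasibility outcome in any of the 160.

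This rests on three readings: that patients in item a means starters, that only the PI or SC performs the SPE, and that the general adverse-event process does not feed item c. The protocol's differing statements on whether the PI or the SC conducts the screening session do not affect the conclusion, since both are study staff, but they should be reconciled.

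**What to change.** 1. Restrict Objective 1 and its conclusion to the feasibility of referral from primary care to a laboratory-based SPE. Label the 80% rule as feasibility of the treatment programme among those who started it. State who conducts the screening session.
2. Extend item c to count adverse reactions to the SPE in all screened participants. Record SPE duration and the share of participants who complete every test.
3. Report yield (eligible/screened) and uptake (starters/eligible) with exact 95% confidence intervals beside completion, and name them as inputs to the triangulation. Do not use 37.5% and 50% as pass marks.
4. Report ease of use separately for those who performed the SPE and those who only referred patients or received its report.

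The cost is protocol wording, a start and stop time, and a short reaction record at a visit that already takes place. The downside is a narrower claim and slightly more recording.

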Participants identified as eligible for allocation to the treatment arm of the study will be booked for their initial treatment session a maximum of 2 weeks following the screening session. Participants will be assessed during the first treatment session using an extended standardised assessment of the cervical spine (1 hour). Additional tests of musculoskeletal [31, 71] and sensorimotor function [72] as well as neural mechanosensitivity [73], standard to physiotherapy clinical practice in management of disorders of the neck and concussion [74], in addition to baseline results (provided in report form via post from the SC and supplied to the treating physiotherapist) will inform individualised treatment plans [18, 75]. Following initial assessment by the therapist, participants will receive treatment twice weekly for 4 weeks. During this time participants will also be requested to avoid alternate treatments for their concussion (except for use of prescribed medication/s) to minimise potential for confounding.

Interventions:

Treatment for management of identified neck impairments provided will include OMT (For e.g., Maitland, and Mulligan intervertebral joint mobilisation techniques) neuromuscular and sensorimotor retraining techniques standard to musculoskeletal physiotherapy practice internationally and in New Zealand for management of neck disorders [18, 75]. Individual treatment plans will be pragmatically determined. All participants receiving treatment will be provided with advice and education relating to graduated return to activity and prescribed a sub-symptom threshold cardiovascular exercise program using previously published

guidelines for exercise intensity dose [76]. This adjunct treatment aligns with internationally accepted standards of best practice for concussion management [4].

Treating physiotherapists, up-skilling, and treatment monitoring:

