We will use Thematic Analysis, an evaluative deductive approach to analyse the qualitative focus group and interview data, as described by Clarke and Braun [77]. The SC will code each transcription and one of the researchers will code every third transcription, grouping the codes into themes and sub-themes. An iterative process will be used within the research team to define the main themes and emerging models related to the study aims. In this way thematic analysis will be reflexive to aid in identification of any instances where the PI's beliefs may unduly influence identification of these main themes.

Quantified feasibility outcomes: activity, compliance, and adverse event monitoring

Participants will record daily performance of home exercises prescribed by the treating therapist in an activity-log (yes/ no, minutes of exercise per day) to determine treatment compliance. Non-attendance at scheduled treatment sessions will be recorded by the treating therapist (yes/no per session) as well as any adverse reactions to treatment (number). Participants will complete an exiting questionnaire to assess patient satisfaction [78].

Experimental Outcomes:

Experimental outcome measures (experimental studies a. & b.) will include but are not limited to:

Category	Exploratory OM
Cervical Spine	

Kinematic Assessment - Virtual Reality	Total range of motion (deg) Peak Velocity – Rotation R (deg/s) Peak Velocity – Rotation L (deg/s) Peak Velocity – Rotation Ext. (deg/s) Global head motion accuracy (deg)
Muscle Function (CFET)	Total time (sec)
Manual Spinal Examination	Pos/ neg
Sensorimotor Function (JPE)	Degrees Error (deg) Neck Disability Index (tot/ 50) Headache Impact Test-6
Vestibulo-Ocular	
VNG OM Assessment	Full Assessment (≥ 2 pos/neg overall (pos/neg) ; pos/neg per assessment)
VOMS assessment	Increase in symptoms (11- point NRS) ; avg NPC > 5cm Dizziness Handicap Index
Participant Outcomes	
Physical Activity : Actigraphy	Minutes of Vigorous Physical Activity, min/day Physical Activity (TAC/d; steps/d; PAEE - kcal/kg/day) Activity log Consensus Sleep Diary PROMIS sleep questionnaires IPAQ (METs) Fatigue Severity Scale
Quality of Life	EuroQol-5D-5L (EQ VAS)

Data Management

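### The 80% adherence mark is a share of exercises, but the home-exercise log, on its natural reading, does not record how many prescribed exercises were done

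*Protocol*

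**What the plan says.** Four places in the protocol bear on this point.

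- **Statistical Analysis, Objective 1, item b** sets the mark: "Adherence will be considered acceptable if 80% of exercises had been recorded", the record being the patient's logbook. The same item names two sources: "Adherence to the intervention by auditing and summarising patients' logbooks and the physiotherapists' assessment and treatment documentation".
- **Quantified feasibility outcomes** (under Outcome Measures and Analysis) describes what patients write down. They record daily performance of "home exercises prescribed by the treating therapist in an activity-log (yes/ no, minutes of exercise per day) to determine treatment compliance". No count of exercises, prescribed or done, is mentioned.
- **Interventions** (under Treatment Sessions) says: "Individual treatment plans will be pragmatically determined". Treatment combines manual therapy with neuromuscular and sensorimotor retraining, and every treated participant is also prescribed a cardiovascular exercise programme. No number of home exercises is given.
- **Objective 1, item a**, directly above, uses a different unit for completion: "The programme will be considered feasible if 80% of patients complete the programme until formal discharge".

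**The concern.** A threshold counted in exercises needs two counts for each patient: exercises prescribed and exercises done. The therapists' records may hold the first. Nothing in the protocol describes a source for the second. If the log has one yes/no for the day, a patient who does part of the programme can tick 'yes' as truthfully as one who does all of it.

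Adherence is one of only two numeric marks under Objective 1, and the Study Objectives list participant compliance among the primary outcomes. The result feeds the overall feasibility judgement and, through it, the design of a later randomised trial. A log that scores partial days as full days would make the programme look better followed than it was. Detail that was never recorded cannot be recovered at analysis.

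**Working it through.** **Plan's own figure.** The 80% is a set threshold with no derivation, so there is nothing to reproduce. The nearest derived numbers are in Study power: 60 × (1 − 0.50) = 30 starting treatment, and 30 × (1 − 0.10) = 27 with data at all time points. Both reproduce, and neither affects this point.

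**Inputs**

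- Treatment period: "participants will receive treatment twice weekly for 4 weeks", so 4 × 7 = 28 days. That exercises are set for every day is an assumption, in line with the daily log.
- Exercises per patient per day, k: not given. Assumed range 1 to 6.
- Meaning of 'yes': not defined. Two readings are tried.

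**Step 1: what the mark needs.** Share of exercises = exercises done / exercises prescribed. For one patient the denominator is 28k. The therapists' documentation could supply it. The numerator needs a count that the log, as described, does not hold.

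**Step 2: 'yes' means any exercise done.** With 'yes' on all 28 days, the patient did between 28 and 28k exercises. The true share therefore lies between 28/(28k) = 1/k and 100%.

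| k per day (assumed) | Log shows | True share of exercises |
|---|---|---|
| 1 | 28/28 | 100% |
| 2 | 28/28 | 50% to 100% |
| 4 | 28/28 | 25% to 100% |
| 5 | 28/28 | 20% to 100% |
| 6 | 28/28 | 17% to 100% |

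For k = 5, one exercise done each day gives 28/28 = 100% on the log against 28/(5 × 28) = 28/140 = 20% of exercises. Only k = 1 fixes the share, and the several components listed under Interventions make k = 1 unlikely for most patients.

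**Step 3: 'yes' means all exercises done.** The distortion reverses. With k = 5 and four done each day, the log shows 0/28 = 0% against (4 × 28)/140 = 112/140 = 80% of exercises. Under this reading the log supports a mark stated in days, but still not one stated in exercises.

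**Step 4: do the minutes help?** Daily minutes convert to a share only if prescribed minutes are known. Even then they give a share of time, so a long spell on one component can stand in for others that were skipped.

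**The case against.** **The log's layout is inferred.** In the sentence on the log, 'per day' may attach only to minutes, and the yes/no may be entered per exercise. The form is not among the appended questionnaires. This stands as a caveat: with one entry per exercise and the prescribed list to hand, the mark could be computed. But the sentence speaks of daily performance and mentions no exercise count, so one entry a day is the natural reading. The protocol should settle it.

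**Other sources are audited.** Item b includes the physiotherapists' documentation, and Data storage says therapists also record information on feasibility. These may supply what was prescribed. No section says they record home performance exercise by exercise, so the missing numerator remains missing.

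**This belongs in an analysis plan.** How a feasibility percentage is aggregated often does. What the log captures does not, since no later plan can restore it.

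**Stronger readings a reader might infer.** One is that the mark can be met while most patients are non-adherent. With equal prescriptions and 30 patients, 16 averaging 62.5% and 14 at 100% give (16 × 0.625 + 14 × 1.0)/30 = 24/30 = 80%. These rates are assumed, and the result needs exercises pooled over patients (with equal prescriptions, the same as averaging their shares). The protocol does not state pooling, and its reference to the patient's own logbooks also allows a per-patient reading. An average of 80% is in any case a legitimate feasibility mark. Pooling can also err the other way: 20 patients with 2 exercises a day at 90% and 10 with 6 a day at 55% (assumed) give (36 + 33)/100 = 69%, a fail with most patients above 80%.

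Another is that patients with longer exercise lists dominate the result. That needs exercise counts, which a log with one yes/no per day would not contain. The two complaints cannot both hold.

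**The stakes are limited.** Item b decides only whether adherence is acceptable. Overall feasibility comes from triangulating qualitative and quantitative results. This is fair.

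**Conclusion.** The point holds as a mismatch between a stated decision threshold and the data described to feed it. The mark is in exercises, while the log on its natural reading gives days and minutes. If 'yes' means any exercise done, a perfect log is compatible with a true share from 1/k to 100%: as low as 20% for five exercises a day, and 50% for two. These figures rest on assumed numbers of exercises, on exercises set daily for 28 days, and on one yes/no entry per day.

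Item b also leaves open whether the 80% is pooled, averaged or applied patient by patient. On the last reading it gives no share of patients who must reach it. That calls for one clarifying sentence. It does not show that the mark would pass with most patients non-adherent.

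The matter is moderate in weight and should be settled before recruitment, because the log cannot be repaired afterwards.

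**What to change.** **Log, before recruitment.** Choose one:

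- one tick per prescribed exercise per day, keeping the mark in exercises; or
- one yes/no per day, with 'yes' defined as all exercises set for that day, and the mark restated in days.

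**Item b.** Define adherence per participant as done divided by prescribed (exercises or days, matching the log), with the denominator taken from the audited therapist documentation. Therapists should be asked to record what was set and for which days, since no section says they do. State whether the 80% applies to the mean of the participants' values or to a proportion of participants reaching it, and if the latter, name the proportion required. Report the number of participants at or above 80% alongside, with an exact 95% confidence interval.

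**Cost.** One line on the log, a sentence or two in item b, and a short instruction to therapists. The per-exercise log is slightly longer for recently concussed patients to complete. The day-based option is shorter but scores a nearly complete day as zero. Either way the mark may be harder to meet.
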